#### **10.5.2.3 Proportion of Symptom resolution**

For each symptom resolution is defined as absent for at least 48 hours. The proportion of subjects with symptom resolution will be analyzed by symptom.

All symptom resolution is defined as all symptoms (those scored 0-3) on the symptom questionnaire scored as absent. The proportion of subjects with all symptom resolution will be analyzed.

These analyses will be performed at Days 7, 14, and 28 by treatment in frequency tables and listed.

In addition, the number of participants that achieve symptom resolution at Days 7, 14, and 28 will be analyzed using logistic regression to compare GT0918 versus placebo if there are sufficient data available.

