		
 ○ With age ≥ 50 years and days from symptom onset to study randomization ≤ 5 days and/or days from the positive SARS-CoV-2 prior to first dosing ≤ 3 days With age ≥ 50 years and higher than normal biomarkers (CRP, Ferritin, D-dimer) • Regarding statistical analysis of viral load, more analyses were added, including two sample t-tests between treatment groups at Days 3, 7, 14, and 28; ANCOVA analysis of change in viral load from baseline at days 3 and 28; and MMRM modeling of change in viral load at day 3, 7, 14, and 28 from baseline. • Added sustained 100% viral reduction and associated statistical analyses of GEE, KM plots, log rank test and Cox regression models. • Added subgroup analysis of primary endpoints based on (1) Days from the Positive SARS-CoV-2 Prior to First Dosing; (2) Biomarker status at baseline; and (3) Common types of viral variants. • More details were added to the time-to-event analysis. • Updated statistical model for viral resistance. • Removed the following analyses 
 ○ Proportion of subjects admitted to an intensive care unit (ICU) due to COVID-19 by Day 28 ○ Days in ICU due to all causes or COVID-19 by Day 28 ○ Time to ICU by Day 28 ○ Proportion of subjects requiring invasive mechanical ventilation or ECMO due to COVID-19 by Day 28 ○ Days on supplemental oxygen/high flow oxygen devices/ invasive mechanical ventilation due to COVID-19 by Day 28 ○ Proportion of subjects with all-cause mortality by Day 28 and Day 42 ○ Proportion of subjects with COVID-19 related mortality by Day 28 and Day 42 • Corrected “RT-PCR” as “ddPCR”. • Removed subgroup analysis of primary endpoint based on Concomitant medication of interest used. • Section 4.10.1.1.3 was added to justify the change in the SAP from the protocol.
2.0	14 Mar 2022	Finalized

LIST OF ABBREVIATIONS

Abbreviation / Acronym	Definition / Expansion
AACR	American Association for Cancer Research
ACE2	Angiotensin Converting Enzyme 2
ACVPU	Alert, Consciousness, Verbal, Pain, Unresponsive Scale
AE	Adverse Event
ALT	Alanine Transaminase
ANC	Absolute Neutrophil Count
aPTT	Activated Partial Thromboplastin Time
AR	Androgen Receptor
ARDS	Acute Respiratory Distress Syndrome
AST	Aspartate Transaminase
ATC	Anatomical Therapeutic Chemical
AUC	Area under the Curve
BID	Twice a Day
BP	Blood Pressure
BMI	Body Mass Index
CDC	Centers for Disease Control and Prevention
CFR	Code of Federal Regulations
CHO	Chinese Hamster Ovary

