
All hospitalization events and COVID-19 related medical attended visits will be listed.

Time to Hospitalization

Time to Hospitalization (in days) is defined as:

First hospital admission date - first dosing date + 1.

Note: Hospitalization (≥ 24 hours) includes Hospitalization, Emergency room and ICU. Extended Care Facility Admittance is excluded.

The following two summaries will be generated separately:

- All-Cause Hospitalization
- COVID-19 Related Hospitalization

If a patient has not experienced hospitalization by completion or early discontinuation of study/study treatment, the patient will be censored at the date of their last visit during the post-treatment period.

Time to hospitalization will be evaluated up to Day 28 and will be summarized and plotted by treatment group with mITT set using the Kaplan-Meier (KM) method. The 2-sided 95% CIs for the 25th, 50th and 75th percentiles, as well as at days 3, 7, 14 and 28 using the Brookmeyer and Crowley method will be reported when estimable. P-value will be obtained from the log-rank test stratified by age, and sex, race and ethnicity, and number of risk factors at randomization. Hazard ratios and corresponding 95% confidence intervals will be obtained from a Cox proportional hazard model which treated treatment group as a unique covariate, and age, and sex, race and ethnicity, and number of risk factors as stratas. The Cox proportional hazard model will be also performed by subgroup of duration since symptom onset to randomization category (≤ 3 days; > 3 days).

If cases of hospitalization are too sparse (e.g., < 1 case in one treatment group), no time to hospitalization analyses will be performed.

Proportion of Symptom Resolution

All symptom resolution is defined as

all symptoms (those scored 0-3*) on the symptom questionnaire scored as absent (scored 0), with each symptom resolution absent for at least 48 hours.

Note: * Seven individual questions from COVID-19-Related Symptom Questionnaire are included here: questions 3, 4, 5, 6, 7, 8 and 9.

Additionally, all symptom resolution will be defined differently to include all individual questions scored 0-3 and related outputs will be noted as sensitivity analysis. It is defined as

all symptoms (those scored 0-3*) on the symptom questionnaire scored as absent (scored 0), with each symptom resolution absent for at least 48 hours.

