Note: * Nine individual questions from COVID-19-Related Symptom Questionnaire are included here: questions 1 through 9.

The proportion of subjects with all symptom resolution will be performed at Days 3, 7, 14, and 28 by treatment in frequency tables and listed using mITT set. Generalized estimating equation (GEE) model will be fitted with the response of symptom resolution mapped to categories of Yes or No and with treatment, age, stratification factors (sex, race and ethnicity, and number of risk factors), time

effect and time*treatment interaction terms included in the model as covariates. Odds ratios with 95% confidence intervals and p-values will be present.

Total symptom score (seven individual questions from COVID-19-Related Symptom Questionnaire included here are questions 3, 4, 5, 6, 7, 8 and 9) and change from baseline in total symptom score to Days 3, 7, 11, 14 and 28 will be summarized by treatment group. Change from baseline will be compared using mixed model repeated measures (MMRM) with the fixed effects of baseline total symptom score, age and stratification factors (sex, race and ethnicity, and number of risk factors) and the random effect of subjects and with time effect and time*treatment interaction terms included in the model. Change from baseline in total symptom score will also be graphically displayed.

Additionally, total symptom score will be calculated differently to include nine individual questions (1 through 9) and related outputs will be noted as sensitivity analysis.

A summary of overall COVID-19 related symptoms, including overall symptoms severity, overall general physical health and returned to usual physical health, at Days 3, 7, 11, 14 and 28 will be provided in frequency table and listed.

Additionally, the proportion of subjects with at least 2 points decrease in symptom score (total of ratings) from baseline to Days 3, 7, 14 and 28 will be summarized and listed as well. Generalized estimating equation (GEE) model will be fitted with the response of at least 2 points decrease mapped to categories of Yes or No and with treatment, age, stratification factors (sex, race and ethnicity, and number of risk factors), time effect and time*treatment interaction terms included in the model as covariates. Odds ratios with 95% confidence intervals and p-values will be present.

Time to All Symptom Resolution

Time to all symptom resolution (in days) is defined as:

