------------	------------	----------------	--------------

6. What was the severity of your muscle or body aches at its worst over the last 24 hours?

None =0	Mild =1	Moderate =2	Severe =3
------------	------------	----------------	--------------

7. What was the severity of your headache at its worst over the last 24 hours?

None =0	Mild =1	Moderate =2	Severe =3
------------	------------	----------------	--------------

8. What was the severity of your chills or shivering at its worst over the last 24 hours?

None =0	Mild =1	Moderate =2	Severe =3
------------	------------	----------------	--------------

9. What was the severity of your feeling hot or feverish at its worst over the last 24 hours?

None =0	Mild =1	Moderate =2	Severe =3
------------	------------	----------------	--------------

10. What was the severity of your Nausea (feeling like you wanted to throw up) at its worst over the last 24 hours?

None =0	Mild =1	Moderate =2	Severe =3
------------	------------	----------------	--------------

11. How many times did you vomit (throw up) in the last 24 hours?

I did not vomit at all =0	1-2 times =1	3-4 times =2	5 or more times =3
------------------------------	-----------------	-----------------	-----------------------

12. How many times did you have diarrhea (loose or watery stools) in the last 24 hours?

I did not have diarrhea at all =0	1-2 times =1	3-4 times =2	5 or more times =3
--------------------------------------	-----------------	-----------------	-----------------------

13. Rate your sense of smell in the last 24 hours:

My sense of smell is THE SAME AS usual=0	My sense of smell is LESS THAN usual =1	I have NO sense of smell =2
--	---	-----------------------------------

14. Rate your sense of taste in the last 24 hours:

My sense of taste is THE SAME AS usual=0	My sense of taste is LESS THAN usual =1	I have NO sense of taste =2
--	---	-----------------------------------

Overall Covid-19-related Symptoms

1. Overall, how bad are your symptoms TODAY (check one)?

No symptoms 	Mild 	Moderate 	Severe 
---	----------------------------------	--------------------------------------	------------------------------------

2. Overall, how is your general physical health today?

Poor 	Fair 	Good 	Excellent 

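### The sensitivity definition of all-symptom resolution claims every item scored 0–3 but lists only Q1–Q9, leaving out nausea, vomiting and diarrhea without a reason

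*SAP*

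**What the plan says.** Protocol 10.5.2.3 sets the endpoint without naming any exclusion: "All symptom resolution is defined as all symptoms (those scored 0-3) on the symptom questionnaire scored as absent". It also plans an item-level analysis: "The proportion of subjects with symptom resolution will be analyzed by symptom".

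SAP 4.10.3 (Proportion of Symptom Resolution) gives two versions. Both refer to symptoms scored 0–3 and require absence for at least 48 hours.

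- **Main version.** Its note reads: "Seven individual questions from COVID-19-Related Symptom Questionnaire are included here: questions 3, 4, 5, 6, 7, 8 and 9".
- **Sensitivity version.** It is introduced by: "all symptom resolution will be defined differently to include all individual questions scored 0-3 and related outputs will be noted as sensitivity analysis". Its note reads: "Nine individual questions from COVID-19-Related Symptom Questionnaire are included here: questions 1 through 9".

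The questionnaire in SAP 6.4 has 14 symptom items. Item 10 asks "What was the severity of your Nausea (feeling like you wanted to throw up) at its worst over the last 24 hours" and is answered from None (0) to Severe (3), the same scale as items 1 to 9. Item 11 (vomiting) and item 12, "How many times did you have diarrhea (loose or watery stools) in the last 24 hours", are frequency items scored 0 to 3. Only items 13 and 14 (smell and taste) stop at 2. Protocol Appendix 5 is the same.

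**The concern.** The label of the sensitivity version and its item list contradict each other, and the three missing items form one group: the gastrointestinal symptoms. The SAP gives no reason for dropping them in 4.10.3 or in the revision history. SAP 4.10.1.1.3, which justifies a change from the protocol, deals only with missing primary-endpoint data.

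A sensitivity analysis on the item set should show whether the choice of items matters. Here both versions leave out the same three items, so neither can. The report would also describe a nine-item result as covering all items scored 0–3, which the SAP's own questionnaire contradicts.

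The omitted items could plausibly behave differently by arm. Protocol 1.3.3 names diarrhea and nausea among the adverse events identified with GT0918 in COVID-19, and Protocol 1.2.3.2 reports gastrointestinal events more often on GT0918 in both the male and female cohorts. Yet these are also listed COVID-19 symptoms (Protocol Appendix 2), which an effective drug could improve. A tolerability effect is plausible mainly while dosing continues (Days 3, 7 and 14), less so at Day 28.

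**Working it through.** **1. Count the items (SAP 6.4).**

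| Items | Response scale | Range | Main version | Sensitivity version |
|---|---|---|---|---|
| Q1–Q2 | None to Severe | 0–3 | no | yes |
| Q3–Q9 | None to Severe | 0–3 | yes | yes |
| Q10 nausea | None to Severe | 0–3 | no | no |
| Q11 vomiting, Q12 diarrhea | frequency | 0–3 | no | no |
| Q13–Q14 smell, taste | same, less, none | 0–2 | no | no |

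The SAP's figure is nine. Three natural rules were tried:

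- every item scored 0–3: 12 items (Q1–Q12);
- only items with None-to-Severe wording: 10 items (Q1–Q10);
- every item: 14.

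None gives nine. Nine is reached only by also dropping Q10–Q12. As shares of the 12 items scored 0–3: main 7/12 = 58%; sensitivity 9/12 = 75%; in neither 3/12 = 25%.

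**2. Does another planned analysis fill the gap?**

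- Total symptom score: Q3–Q9, with a nine-item version that is correctly labelled as nine.
- Item-based symptom improvement: Q3–Q9.
- Decrease of at least 2 points: no item set stated.
- By-symptom resolution: planned in Protocol 10.5.2.3, absent from SAP 4.10.3, and not in the revision-history list headed "Removed the following analyses".
- Full questionnaire: the SAP commits to summarizing it at baseline only (4.6).

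**3. What the omission could do to the result.** For one arm and visit, let *g* be the proportion who meet the nine-item definition but would fail a twelve-item one because of Q10, Q11 or Q12. Then

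twelve-item resolution = nine-item resolution − *g*,

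so the difference between arms (GT0918 minus placebo) shifts by −(*g*_GT0918 − *g*_placebo). One point of difference in *g* is one point in the result: 0.01 × 334 = 3.3 subjects per arm (668 randomized 1:1, SAP 3.1).

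For scale, the standard error of a difference in proportions is √(2p(1−p)/334):

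- p = 30% or 70%: √(0.42/334) = 3.55 points;
- p = 50%: √(0.50/334) = 3.87 points.

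The documents do not give *g*. If its arm difference lay between −5 and +5 points (an assumption, not an estimate), the result would shift by +5 to −5 points, at most 5/3.87 = 1.29 to 5/3.55 = 1.41 standard errors either way.

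**4. Do the earlier data fix the sign?** In the female cohort (76 vs 102, Protocol 1.2.3.2), using √(p₁(1−p₁)/76 + p₂(1−p₂)/102):

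- diarrhea 17% vs 10%: +7.0 points, 95% CI −3.3 to 17.3;
- nausea 12% vs 6%: +6.0 points, 95% CI −2.6 to 14.6.

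Both intervals include zero. These are adverse-event incidences in any subject, not gastrointestinal symptoms persisting after the other nine have cleared. They do not settle the direction.

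**The case against.** The strongest reply is that the item set is clear. Q1–Q9 is written out here and used again for the total score, so the author probably meant nine items and used one loose word; deleting that word and adding a reason would be enough. Protocol 10.1 also lets the SAP override the protocol. The mismatch itself is not in dispute. The override clause settles differences between the two documents, not a conflict between adjacent statements in the SAP. Relabelling would make the text accurate but would still leave no analysis that tests the omission.

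A second reply is that gastrointestinal symptoms are captured elsewhere. In part that is true: all questionnaire records are listed (SAP 4.2), vomiting on treatment must be entered as an adverse event (Protocol 6.1.1.1), and overall symptom severity is tabulated over time. None of these tests the item set. Protocol 8.1.2 also exempts expected disease symptoms from adverse-event reporting unless they are more severe than expected, and the special-interest terms in SAP 6.5 do not include nausea, vomiting or diarrhea.

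Three points stand. The ±5-point range is only an illustration, and the planned model is an adjusted GEE odds ratio rather than a raw difference. The revision history records changes between SAP versions, so its silence on the by-symptom analysis proves little; the status of that analysis is simply unclear. And the main Q3–Q9 set departs further from the protocol than the sensitivity set does.

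**Conclusion.** The concern holds. Under the SAP's own questionnaire the label means 12 items, the list has 9, and no reading of the label gives 9. Followed as written, a subject with continuing nausea, vomiting or diarrhea can count as having all symptoms resolved in both the main and the sensitivity analysis.

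The item count is certain and rests on no assumption: 3 of 12 items (25%) are in neither version. The effect on the treatment comparison is unknown in sign and size; the figure of up to about 1.3–1.4 standard errors rests wholly on the assumed ±5 points. Only secondary symptom endpoints are affected. This should be corrected, but it does not threaten the trial's main conclusion.

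**What to change.** - **Sensitivity item set.** In SAP 4.10.3, change the list from questions 1–9 to questions 1–12, and state that the same set applies to a sensitivity version of time to all-symptom resolution, which the SAP does not now make explicit.
- **By-symptom resolution.** Add the analysis planned in Protocol 10.5.2.3, including Q10–Q12, by arm and visit.
- **Main definition.** The seven-item set may stay if the SAP gives a reason for departing from Protocol 10.5.2.3.
- **If Q1–Q9 is kept.** Drop the claim to cover all items and give the reason. The by-symptom table would then be the only place where the omission could be seen.
- **Optional.** For consistency, add twelve-item versions of the total score and the item-based improvement analysis, and state the item set for the 2-point decrease.

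The cost is a wording change, a rerun of existing programs with three items already collected daily, and one further table. Symptom results may move in either direction.

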4.6 Demographic and Other Baseline Characteristics

Demographic and other baseline characteristics will be summarized by treatment group using the ITT set. The summaries provided will include the following:

- Demography
 - Age in years, age group (<50 years; \geq 50 years), age group (<60 years; \geq 60 years), and age group (<65 years; \geq 65 years)
 - Sex
 - Race
 - Ethnicity
 - Baseline height
 - Baseline weight
 - Baseline BMI
 - Baseline BMI categories as below
 - Underweight (<18.5)
 - Normal (\geq 18.5 and <25.0)
 - Overweight (\geq 25.0 and <30.0)
 - Obesity (\geq 30.0)
 - Obesity Class 1 (\geq 30.0 and < 35.0)
 - Obesity Class 2 (\geq 35.0 and < 40.0)
 - Obesity Class 3 (\geq 40.0)
- Other Baseline Characteristics
 - Days from the positive SARS-CoV-2 prior to first dosing and test type
 - Days from onset of COVID-19 symptoms prior to first dosing
 - Prior COVID-19 therapy
 - Number of high-risk medical factors (0; 1-2; \geq 3)
 - High-risk medical status by below categories
 - Age \geq 65 years
 - Cancer
 - Chronic kidney disease
 - Chronic lung diseases
 - Chronic obstructive pulmonary disease
 - Asthma
 - Interstitial lung disease
 - Cystic fibrosis
 - Pulmonary hypertension
 - Dementia or other neurological conditions
 - Dementia

- Other
- Down syndrome
- Heart conditions
 - Heart failure
 - Coronary Artery Disease
 - Cardiomyopathies
 - Hypertension
- Immunocompromised state (weakened immune system) from solid organ transplant
- Liver disease
- Overweight and Obesity (BMI ≥ 25 kg/m²)
 - Overweight (BMI ≥ 25.0 kg/m² and < 30.0 kg/m²)
 - Obesity (BMI ≥ 30.0 kg/m² and < 40.0 kg/m²)
 - Sever Obesity (BMI ≥ 40.0 kg/m²)
- Sickle cell disease or Thalassemia
 - Sickle cell
 - Thalassemia
- Smoking (current or former)
 - Current
 - Former
- Diabetes (type 1 or type 2)
 - Type 1
 - Type 2
- HIV infection
- Solid organ or blood stem cell transplant
 - Solid organ transplant
 - Blood stem cell transplant
- Stroke or cerebrovascular disease, which affects blood flow to the brain
 - Stroke
 - Cerebrovascular disease
- Substance use disorders
- Other

- Medical history will be reported by system organ class (SOC) and preferred term (PT) as coded using the Medical Dictionary for Regulatory Activities (MedDRA) Version 24.0 or higher.
- Medication allergy history will also be reported by SOC and PT separately.
- Baseline patient reported COVID-19 symptom questionnaires will be summarized.

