First date when all symptom resolution status is changed to 'Yes' - first dosing date + 1.

If a patient has not experienced symptom resolution by completion or early discontinuation of study/study treatment, the patient will be censored at the date of their last visit during the post-treatment period.

Time to all symptom resolution will be applying the same KM methods and Cox proportional hazard models introduced in the time to hospitalization section.

Symptom Improvement

Symptom improvement is defined as a change in severity of overall symptoms * from a higher score to a lower score, which is defined as following:

symptoms scored as moderate or severe at baseline are scored as mild or absent,
OR

symptoms scored as mild or absent at baseline are scored as absent.

Note: * The overall symptoms question (overall question 1) under overall COVID-19 related symptoms from COVID-19-Related Symptom Questionnaire is included here.

Additionally, symptom improvement will be defined by individual symptom questions from symptom questionnaire as below and related outputs will be noted as sensitivity analysis. It is defined as a patient experiencing both:

symptoms * scored as moderate or severe at baseline are subsequently scored as mild or absent,

AND

symptoms * scored as mild or absent at baseline are subsequently scored as absent.

Note: * Seven individual questions from COVID-19-Related Symptom Questionnaire are included here: questions 3, 4, 5, 6, 7, 8 and 9.

The proportion of subjects with symptom improvement at Days 3, 7, 11, 14 and 28 will be summarized by treatment in frequency tables and listed using mITT set. Generalized estimating equation (GEE) model is fitted with the response of symptom improvement mapped to categories of Yes or No and with treatment, age, stratification factors (sex, race and ethnicity, and number of risk factors), time effect and time*treatment interaction terms included in the model as covariates. Odds ratios with 95% confidence intervals and p-values will be present.

Time to Symptom Improvement

Time to symptom improvement (in days) is defined as:

Date when symptom improvement status is changed to 'Yes' - first dosing date + 1.

If a patient has not experienced symptom improvement by completion or early discontinuation of study/study treatment, the patient will be censored at the date of their last visit during the post-treatment period.

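### The SAP's sensitivity analysis of symptom resolution claims every question scored 0-3 but stops at Q9, leaving out nausea, vomiting and diarrhea, so the protocol's definition is never analysed

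*SAP*

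**What the plan says.** Protocol 10.5.2.3 sets the definition: "All symptom resolution is defined as all symptoms (those scored 0-3) on the symptom questionnaire scored as absent". The same section adds an analysis of each symptom separately: "The proportion of subjects with symptom resolution will be analyzed by symptom". Both are planned by treatment at Days 7, 14 and 28.

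SAP 4.10.3 narrows the main definition to seven items: "Seven individual questions from COVID-19-Related Symptom Questionnaire are included here: questions 3, 4, 5, 6, 7, 8 and 9". It then announces a wider sensitivity version, in which "all symptom resolution will be defined differently to include all individual questions scored 0-3". The note to that version reads: "Nine individual questions from COVID-19-Related Symptom Questionnaire are included here: questions 1 through 9". The total symptom score follows the same pattern. Its main form uses Q3-Q9, and for the sensitivity form "total symptom score will be calculated differently to include nine individual questions (1 through 9".

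The questionnaire in SAP Appendix 6.4 (Protocol Appendix 5) continues past Q9. Q10 asks about the severity of nausea, Q11 counts vomiting, and Q12 asks "How many times did you have diarrhea (loose or watery stools) in the last 24 hours". Each of these three has four response options scored 0 to 3. Only Q13 (smell) and Q14 (taste) are scored 0 to 2.

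Protocol 10.1 lets the SAP prevail where the two documents differ.

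**The concern.** The sensitivity analysis is described in one way and specified in another. A reader of the results would take it as the version covering all the 0-3 symptoms, which is the protocol's definition, and it is not.

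The missing items are not arbitrary for this drug. Protocol 7.2.1.3 lists nausea, vomiting and diarrhea among the questionnaire symptoms of COVID-19, and Protocol 1.3.3 names diarrhea and nausea among the adverse events identified with GT0918. A resolution endpoint that cannot see them may label as recovered a subject who still has a symptom of the disease or an effect of the treatment. Because the main and the sensitivity definitions both leave them out, comparing the two would not show whether the result depends on these items.

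**Working it through.** **1. Reproduce the plan's count of nine.** Inputs are the response options in SAP Appendix 6.4.

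- Q1-Q10, worded None / Mild / Moderate / Severe, scored 0-3: 10 items.
- Q11-Q12, frequency bands, scored 0-3: 2 items.
- Q13-Q14, scored 0-2: 2 items.

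Questions scored 0-3: 10 + 2 = **12**. Counting only those worded as severities gives 10. Neither count gives the 9 in the SAP note.

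**2. Size of the gap.**

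| Set | Items | Maximum score |
|---|---|---|
| SAP main, Q3-Q9 | 7 | 7 × 3 = 21 |
| SAP sensitivity, Q1-Q9 | 9 | 9 × 3 = 27 |
| All questions scored 0-3, Q1-Q12 | 12 | 12 × 3 = 36 |

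Omitted from the larger SAP set: 12 − 9 = 3 items (Q10, Q11, Q12), worth 36 − 27 = 9 points, and 9/36 = 25% of the scale.

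**3. Is Q10-Q12 picked up by another post-baseline outcome in SAP 4.10.3?**

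- All-symptom resolution: Q3-Q9 (main), Q1-Q9 (sensitivity). Time to resolution is built on the same status.
- Total symptom score: Q3-Q9 (main), Q1-Q9 (sensitivity).
- Symptom improvement: overall question 1 (main), Q3-Q9 (sensitivity).
- Decrease of at least 2 points: a total of ratings with no items named. As a total, it cannot show a single symptom.
- Resolution symptom by symptom, as in Protocol 10.5.2.3: no counterpart in the SAP.

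SAP 4.2 does refer to questions 1 through 14, but only to choose between duplicate records. No item set that the SAP names for post-baseline analysis contains Q10-Q12.

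**4. Consequence for one subject.** Take a subject with 0 on Q1-Q9 for at least 48 hours and a score of 1 on Q10. The subject is resolved under Q3-Q9 and under Q1-Q9, and not resolved under Protocol 10.5.2.3. No extreme score is needed.

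**5. Consequence for the comparison.** At a given visit, let d be the share of an arm with Q1-Q9 absent and any of Q10-Q12 present. The Q1-Q9 resolution proportion equals the Q1-Q12 proportion plus d. The treatment difference therefore shifts by d(GT0918) − d(placebo). The documents give d for neither arm. Adverse event percentages from the earlier COVID-19 outpatient trial cannot stand in for it, because they do not count subjects whose other symptoms have gone.

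**The case against.** **The note governs.** One can say that a programmer will follow the explicit list, so the specification is clear and only the lead-in is loose. That the list would be followed is true, but it does not help. Q1-Q9 is then what is analysed, and the protocol's definition is still missing. The SAP gives no reason for stopping at Q9; its section justifying a departure from the protocol (4.10.1.1.3) concerns missing primary assessments only.

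**Other analyses give partial cover.** Overall question 1 asks how bad the subject's symptoms are and excludes none, so gastrointestinal symptoms can affect main symptom improvement and the overall-severity table. The 2-point-decrease outcome might include Q10-Q12. The protocol's symptom-by-symptom analysis might also survive, since SAP silence is not plainly a difference. All this is fair, but none of it is all-symptom resolution on Q1-Q12, and no SAP output carries the symptom-by-symptom analysis.

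**A reader might infer that these symptoms appear in no by-arm table at all.** The documents do not support that. SAP 4.6 states "Baseline patient reported COVID-19 symptom questionnaires will be summarized", by treatment group and without restricting items. SAP 4.11 and 4.11.2 tabulate treatment-emergent adverse events by preferred term and by arm. Protocol 6.1.1.1 requires vomiting during treatment to be entered in the adverse event pages. The gap is narrower: no SAP-specified post-baseline by-arm table shows the questionnaire items Q10-Q12 individually.

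**A reader might also infer that the safety tables will hide a gastrointestinal harm.** Protocol 8.1.2 exempts expected disease symptoms unless they are more severe than expected, so some nausea or diarrhea could go unreported as adverse events. That is a possibility of unknown size and direction. In the earlier COVID-19 trial, adverse event reporting in women did show a difference (diarrhea 17% vs. 10%, nausea 12% vs. 6%, GT0918 vs. control; Protocol 1.2.3.2), although the documents do not say whether its reporting rules were the same.

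**Conclusion.** The SAP text is wrong as written. Its sensitivity set for all-symptom resolution is described as every question scored 0-3 and lists 9 of 12, and the sensitivity total score has the same cut-off. Protocol 10.5.2.3's definition is consequently analysed nowhere in the SAP. This rests only on counting response scales and needs no assumption.

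The effect on results is not known. It would be tempting to say that the omission favours GT0918 because nausea and diarrhea are named drug effects. It would do so if, among subjects otherwise free of symptoms, these complaints were commoner on GT0918; if the drug relieved them, the omission would work against it. The documents do not settle which.

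The point concerns sensitivity versions of secondary endpoints. The primary endpoint, the interim rules and the sample size are unaffected. It still deserves correction, because it changes what the sensitivity analyses measure and costs almost nothing to put right.

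**What to change.** In SAP 4.10.3, change the sensitivity item set from Q1-Q9 to Q1-Q12 in two places: all-symptom resolution (which carries through to time to resolution) and total symptom score. Leave the main Q3-Q9 analysis unchanged. The cost is two edits to the text and the matching programming, using daily questionnaire data that are already collected. The maximum of the sensitivity total rises from 27 to 36.

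Optional, and not needed for the point to stand: a descriptive by-arm table of post-baseline worsening on Q10, Q11 and Q12 separately, for Days 2-14 and 15-28. It should start at Day 2 because the items look back 24 hours, which makes a Day 1 record largely pre-dose. It should give the number of questionnaire days completed per arm and window, because the chance of any worse day rises with the number of days completed.

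A note should say that the table covers outpatient days only, shows the net of drug and disease effects, and does not exclude harm if null. On that last point, take equal rates p in both arms and 334 per arm (668/2). The 95% half-width for the difference is 1.96 × √(2p(1−p)/334): 4.6 points at an assumed p of 10% and 7.6 points at 50%. The documents do not give these rates.
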